3.5 Additional Endpoints

Not applicable.

4.0 Analysis Populations

The following population sets will be used for the analyses.

The Intent-to-Treat (ITT) Population includes all randomized subjects. For the DB period analyses, subjects will be included in the analysis according to the treatment groups to which they were randomized. For the OL period analyses, data will be analyzed according to the treatments randomized in the DB period and received in the OL period (i.e., AGN-151586/AGN-151586, AGN-151586/None, Placebo/AGN-151586, Placebo/None).

Baseline analyses and efficacy analyses for US FDA and EU Regulatory agencies will be performed on the ITT population, consisting of all randomized subjects. Subjects will be included in the DB period analysis according to the treatment groups to which they were randomized. For the OL period analyses, data will be analyzed according to the treatments randomized in the DB period and received in the OL period, as above.

Additionally, for EU regulatory agencies only, subgroup analyses will be performed on the ITT population that also has a baseline FLO-11 total score (transformed) ≤ 50 . Analyses will consist of the EU coprimary and key secondary endpoints.

The Safety Population consists of all subjects who were treated with at least 1 dose of study drug (i.e., AGN-151586 or placebo). All safety analyses will be performed with subjects analyzed by their actual treatment received in the DB period/OL period (i.e., AGN-151586/AGN-151586, AGN-151586/None, Placebo/AGN-151586, Placebo/None), and will be presented with overall safety data for the study (i.e., either period), for DB period, and for OL period. The Safety Population will be used for all safety analyses.

5.0 Subject Disposition

The total number of subjects who were screened, enrolled (randomized), and treated will be summarized for the ITT population. A summary of subject accountability will be provided where the number of subjects in each of the following categories will be summarized for each treatment group and for the DB period and the OL period:

- Subjects enrolled (randomized) in the study;
- Subjects treated with at least one dose of study drug;
- Subjects who completed the study;
- Subjects who prematurely discontinued study (with reason),

Subjects in each analysis population will also be summarized.

For end of study participation, the number and percentage of subjects who completed the protocol defined follow-up period will be summarized overall and by treatment group.

6.0 Study Drug Duration and Compliance

For the Safety Population, the number of subjects treated will be presented by treatment group for the double-blind period, as well as the open-label period. Duration on treatment is assumed for the duration of the study period or until study exit. If a subject does not receive the full dose, this will be indicated; significant deviations to dosing will be reported.

7.0 Demographics, Baseline Characteristics, Medical History, and Prior/Concomitant Medications

Demographics, baseline or disease characteristics, medical history, prior and concurrent procedures, and prior and concomitant medications will be summarized for the ITT population overall and by treatment group. Categorical variables will be summarized with the number and percentage of subjects; percentages will be calculated based on the number of non-missing observations. Continuous variables will be summarized with descriptive statistics (number of non-missing observations, mean and standard deviation, median, Q1, Q3, minimum and maximum).

7.1 Demographics and Baseline Characteristics

Demographics and baseline characteristics will be summarized descriptively, overall and by treatment group. Unless otherwise specified, baseline is defined as the last non-missing value prior to the first administration of study drug.

Continuous demographic variables include age, weight, height, and body mass index (BMI). Continuous baseline characteristic variables include FLO-11 total scores (transformed) and item scores (for items 1-10), and FLSQ treatment expectations and impact domain scores.

Categorical demographic and baseline characteristic variables include:

- Sex
- Ethnicity (Hispanic or Latino, Not Hispanic or Latino)
- Race
- Age (< 65, \geq 65 years)
- Region (North America, EU)
- BMI (< 25, \geq 25 kg/m²).
- Nicotine user (current, former, never, unknown)
- Alcohol user (current, former, never, unknown)
- Prior aesthetic toxin use (prior use, no prior use)
- FWS at maximum frown
 - As assessed by investigator
 - As assessed by subject
- FWS at rest
 - As assessed by investigator
 - As assessed by subject
- FLO-11 total score (transformed) (\leq 50, $>$ 50)
- FLSQ item scores
- Fitzpatrick Skin Type

7.2 Medical History and Prior and Concurrent Procedures

Medical history data will be reported and summarized separately from prior procedures data for the ITT population. Medical history data and prior procedure data will be coded using the Medical Dictionary for Regulatory Activities (MedDRA). The actual version of the MedDRA coding dictionary will be noted in the statistical tables and clinical study report. The number and percentage of subjects in each medical history category (by MedDRA system organ class and preferred term) will be summarized overall and by treatment group. Similarly, the number and percentage of subjects in each prior procedures category will be summarized overall and by treatment group. The system organ class (SOC) will be presented in alphabetical order, and the preferred terms will be

presented in alphabetical order within each SOC. Subjects reporting more than one condition/diagnosis will be counted only once in each row (SOC or preferred term).

In addition, any concurrent procedures, defined as any procedure performed on or after the date of first treatment, will be summarized by term in each treatment group for the ITT population.

7.3 Prior and Concomitant Medications

Prior and concomitant medications will be summarized by generic name for the ITT population. A prior medication is defined as any medication taken prior to the date of the first dose of study drug. A concomitant medication is defined as any medication that started prior to the date of the first dose of study drug and continued to be taken after the first dose of study drug or any medication that started on or after the date of the dose of study drug, but not after the date of the last visit assessment. The number and percentage of subjects taking medications will be summarized by generic drug name based on the World Health Organization (WHO) Drug Dictionary for both prior and concomitant medications.

8.0 Handling of Potential Intercurrent Events for the Primary and Key Secondary Endpoints

The primary composite and coprimary endpoints for the US FDA and for the EU regulatory agencies (defined in Section 3.1), respectively, will be analyzed based on the ITT population, and the following methods will be used to address potential intercurrent events:

- Subjects who did not receive any dose of study drug but are randomized will still be included in the ITT population. For the EU, those who also had baseline FLO-11 total score (transformed) of ≤ 50 will be included in subgroup analyses of the coprimary and key secondary endpoints.
- Subjects who are randomized but prematurely discontinued the study before assessment of the primary composite or coprimary endpoints will be considered as part of the ITT population.

- Subjects who die before assessment of the primary composite or coprimary endpoints will count as though they hypothetically continued in the study.
- Subjects who are lost to follow-up and are missing data for the primary composite or coprimary endpoints will count as though they hypothetically continued in the study.
- Subjects who are missing assessments or data due to the COVID-19 pandemic and are missing data for the primary composite or coprimary endpoints will count as though they hypothetically continued in the study.
- Subjects who are missing data for any other reason for the primary composite or coprimary endpoints will count as though they hypothetically continued in the study.

The secondary efficacy analysis of secondary endpoints (defined in Section 3.2) will be analyzed based on the same populations as above with similar methods for addressing potential intercurrent events.

9.0 Efficacy Analyses

9.1 General Considerations

All efficacy analyses will be conducted in the ITT Population for the US and EU regulatory agencies.

Analyses for the DB period will be conducted using a gated hierarchical testing procedure to preserve a familywise Type I error rate of $\alpha = 0.05$. DB treatment groups will be AGN-151586 and placebo. Analyses for the OL period will be performed outside of the testing hierarchy. Treatment groups reported for the OL period will include both the DB and OL period treatment group combinations (i.e., AGN-151586/AGN-151586, AGN-151586/None, Placebo/AGN-151586, Placebo/None).

For the DB period, to control the family-wise Type I error rate at 0.05 for multiplicity across the primary and secondary analyses, a hierarchical testing strategy¹ will be used. The hierarchical testing strategy starts with the primary efficacy endpoint followed by

sequential testing of the secondary endpoints, in the order listed for the US and EU regulatory agencies, respectively (see Section 13.0). Statistical significance will be evaluated in order. If statistical significance at the 0.05 alpha level (2-sided testing) is shown for the first variable in the ranking order, then the next variable in the immediate subsequent order will be evaluated for statistical significance. If statistical significance is shown for the second variable in the ranking order, then the analysis will continue in the same manner for subsequent variables. If no statistical significance is shown at the 0.05 alpha level for any variable in the ranking order, then that variable and all subsequent variables will not be considered statistically significant, regardless of their p-values. Nominal p-values will then be provided.

[figure not shown]
[figure not shown]
The Primary Analysis will be performed after all ongoing subjects have completed both the DB period and the OL period and the database has been locked. This will be the only and final analysis for the composite, coprimary and secondary efficacy endpoints, as well as all other efficacy endpoints in the DB period. Descriptive analyses will be provided for the OL period measures over time.

Unless otherwise specified, categorical variables will be analyzed using Cochran-Mantel-Haenszel (CMH) test, [REDACTED] [REDACTED]. Continuous variables will be analyzed using analysis of covariance (ANCOVA) [REDACTED] [REDACTED].

A subject who is randomized based on a wrong stratum will be analyzed according to the subject's actual stratum. However, if a subject has a baseline FWS lower than moderate severity at maximum frown, then the subject will be included in stratified analyses within the moderate GL severity at maximum frown stratum. In analyses not stratified by baseline FWS, the observed baseline FWS will be used.

For efficacy analyses of FWS assessments, “baseline” refers to the last non-missing observation before either the first administration of study drug or randomization if no study drug is given or the administration of study drug during retreatment. The change

[figure not shown]
from baseline values will be computed as the post-baseline value minus the observed baseline value.

9.2 Handling of Missing Data

Missing data will be imputed for the DB Period only using the following methods for the efficacy analyses:

- Multiple Imputation: The Multiple Imputation approach will be used as a primary analysis for the primary endpoint, as well as for all secondary endpoints.

- Non-responder Imputation (NRI): The NRI analysis will categorize any subject who does not have evaluation during a specific visit window as a non-responder for that visit. The NRI will be one of the sensitivity analysis approaches in the analyses of categorical variables for the primary efficacy endpoints.
- As Observed (AO): The AO analysis will not impute values for missing evaluations, and thus a subject who does not have an evaluation on a scheduled visit will be excluded from the AO analysis for that visit. AO will include all values collected in the study and will be used for sensitivity analyses for the primary efficacy endpoints.

9.3 Primary Efficacy Endpoints and Analyses

9.3.1 Primary Efficacy Endpoints

The assessments of the severity of GL at maximum frown using the validated FWS is based on the following scale (for both investigator and subject):

- 0 = None
- 1 = Mild
- 2 = Moderate
- 3 = Severe

The primary composite endpoint for FDA is the following:

- A Grade 0 or 1 (none or mild) and at least a 2-grade improvement from baseline on the FWS according to both investigator and subject assessments of GL severity at maximum frown at Day 7

The coprimary endpoints for EU regulatory agencies are the following:

- \geq 2-grade improvement from baseline on the FWS according to subject assessment of GL severity at maximum frown at Day 7, and

- \geq 2-grade improvement from baseline on the FWS according to investigator assessment of GL severity at maximum frown at Day 7.

9.3.2 Main Analysis of Primary Efficacy Endpoints

The attributes of the estimands corresponding to the primary efficacy endpoints for the US FDA and EU regulatory agencies are summarized in [Table 1](#). In addition, the attribute of treatment is a single dose of AGN-151586 or placebo.

US FDA: The primary composite responder endpoint for a Grade 0 or 1 (none or mild) and at least a 2-grade improvement will be analyzed using the CMH method [REDACTED]

[REDACTED]. The primary composite endpoint must meet $p \leq 0.05$ to be considered successful.

EU regulatory agencies: The coprimary responder endpoints for \geq 2-grade improvement from baseline in the FWS will be analyzed separately using the CMH method [REDACTED]

[REDACTED]. Both coprimary endpoints must meet $p \leq 0.05$ to be considered successful.

The evaluation of the equality of the proportions of responders for the primary composite or coprimary endpoints at Day 7 will be based on the CMH test [REDACTED]

[REDACTED]. The 95% confidence interval for the treatment responder rate differences will be constructed using the normal approximation to the binomial distribution.

Table 1. Summary of the Estimand Attributes of the Primary Efficacy Endpoints

[figure not shown]
Estimand Label	Attributes of the Estimand			
	Variable (Endpoint)	Population	Handling of Intercurrent Events	Statistical Summary
Hypothetical estimand for primary composite endpoint (US FDA)	Achievement of a Grade 0 or 1 (none or mild) and at least a 2-grade improvement from baseline on the FWS according to both the investigator and subject assessments (composite) of GL severity at maximum frown on Day 7	Intent-to-treat (ITT) (all randomized)	Subjects who discontinue study prior to Day 7 assessments, or who do not have FWS assessments will be included in the analysis as a hypothetical scenario in which they had not missed the FWS assessments	Response rates and rate differences between AGN-151586 and placebo treatment groups; Cochran-Mantel-Haenszel (CMH) test
Hypothetical estimand for coprimary endpoints (EU)	Achievement of at least a 2-grade improvement from baseline on the FWS according to: 
 • Subject's assessment of GL severity at maximum frown at Day 7, and • Investigator's assessment of GL severity at maximum frown at Day 7 	ITT	Subjects who discontinue study prior to Day 7 assessments, or who do not have FWS assessments will be included in the analysis as a hypothetical scenario in which they had not missed the FWS assessments	Response rates and rate differences between AGN-151586 and placebo treatment groups; CMH test

CMH = Cochran-Mantel-Haenszel; EU = European Union; FDA = Food and Drug Administration; FWS = Facial Wrinkle Scale; GL = Glabellar lines; ITT = intent-to-treat; US = United States

9.3.3 Sensitivity and Supplementary Analyses of the Primary Efficacy Endpoints

Sensitivity analyses of the primary efficacy variables will be performed to establish their consistency and robustness as well as to further characterize the extent of subjects'

responses. As-observed data analysis, as well as missing as non-responder (using NRI) analysis, [REDACTED] for sensitivity analyses.

9.4 Secondary Efficacy Endpoints and Analyses

9.4.1 Secondary Efficacy Endpoints

Analysis of the secondary endpoints will be conducted on the ITT population based on treatment as randomized for the US FDA and EU regulatory agencies.

Secondary efficacy endpoints for the US FDA and EU regulatory agencies are listed in Section 3.2, and include other response definitions for the FWS by investigator and subject, as well as for the FLO-11, FLSQ, and GAC-GL.

[figure not shown]
The FLO-11, FLSQ, and GAC-GL instruments are described below.

FLO-11: The FLO-11 is a validated 11-item COA instrument to assess emotional and appearance-related impacts of upper facial lines from a subject's perspective. Each item is on an 11-point numeric rating scale that ranges from 0 (not at all) to 10 (very much) with a middle label of somewhat. For scoring, all items are transformed to a 0 to 100 scale, with higher scores indicating better outcomes. Total score is calculated as the sum of the reverse score (i.e., 10 minus the original score) of Items 1 to 10 plus the raw score of Item 11 (Item 11 does not need to be a reverse score). Total scores are transformed to a 0 (worst) to 100 (best) point scale by setting the lowest and highest possible scores at 0 and 100, respectively; these are the transformed scale scores. The 50% rule is applied for the total score, such that scales with at least 50% non-missing item responses will be scored as the average of the non-missing responses. If the total scale is missing more than 50% of the item responses, then the total scale score will be set as missing.

FLSQ: The FLSQ consists of 2 versions (baseline and follow-up versions) to assess study intervention (i.e., treatment) expectations, treatment satisfaction, and impact of hyper functional upper facial lines (LCL, forehead lines, and/or GL). The baseline version consists of 11 items (2 multi-item domains: treatment expectations and impact), while the follow-up version consists of 13 items (2 multi-item domains: treatment satisfaction, and impact; 3 single item domains: met treatment expectations, continue treatment, and recommend to others). Additionally, FLSQ follow-up items 2, 3, 4, 5, 9, and 11 are

validated for use as stand-alone items.

GAC-GL: The GAC-GL is a 2-item measure that assesses the appearance of the subject's GL "now" in comparison with their perspective before treatment at rest and at maximum frown. The response options are scored on a 7-point numerical rating scale ranging from *Very much improved* to *Very much worse*. Scores are unique for at rest and maximum contraction, and they are simply the responses to the items.

9.4.2 Main Analyses of Secondary Efficacy Endpoints

The attributes of the estimands corresponding to the secondary efficacy endpoints are summarized in [Table 2](#). Analysis of the secondary endpoints will be conducted on the ITT population based on treatment as randomized for the US FDA and EU regulatory agencies.

[figure not shown]
[figure not shown]
For the secondary endpoints, the proportion of responders will be analyzed using the CMH test [REDACTED]. The continuous variables will be analyzed using ANCOVA [REDACTED]

Table 2. Summary of the Estimand Attributes of the Secondary Efficacy Endpoints

Estimand Label	Attributes of the Estimand		
	Variables (Endpoints)	Handling of Intercurrent Events	Statistical Summary
Hypothetical estimand for key secondary categorical endpoints (US FDA)	
Key (US FDA): Achievement of a Grade 0 or 1 (none or mild) and at least a 2-grade improvement from baseline on the FWS according to:
 
 both the investigator and subject assessments (i.e., concurrent composite) of GL severity at maximum frown over time (DB period)*, investigator assessment of GL severity at maximum frown over time (DB period)*, subject assessment of GL severity at maximum frown over time (DB period)* 	Subjects who discontinue study in the DB period, or who do not have FWS assessments will be included in the analysis as a hypothetical scenario in which they had not missed the FWS assessments	Response rates and rate differences between AGN-151586 and placebo treatment groups at each time point; CMH test [REDACTED] [REDACTED] [REDACTED] Endpoints will be evaluated outside of the gated hierarchical testing.
Hypothetical estimand for secondary categorical endpoints (EU)	Achievement of at least a 2-grade improvement from baseline on the FWS according to: 
 investigator assessment of GL severity at maximum frown over time (DB period)*, subject assessment of GL severity at maximum frown over time (DB period)* 	Subjects who discontinue study in the DB period, or who do not have FWS assessments will be included in the analysis as a hypothetical scenario in which they had not missed the FWS assessments	Response rates and rate differences between AGN-151586 and placebo treatment groups at each time point; CMH test [REDACTED] [REDACTED] [REDACTED] Endpoints will be evaluated outside of the gated hierarchical testing.

Estimand Label	Attributes of the Estimand		
	Variables (Endpoints)	Handling of Intercurrent Events	Statistical Summary
Hypothetical estimand for secondary categorical endpoints (EU only)	
Achievement of at least a 2-grade improvement from baseline in GL severity at maximum frown based on:
 
 • Subject assessment using FWS at Hour 24 • Investigator assessment using FWS at Hour 24 	Subjects who discontinue study prior to Hour 24 assessments, or who do not have FWS assessments will be included in the analysis as a hypothetical scenario in which they had not missed the FWS assessments	
Response rates and rate differences between AGN-151586 and placebo treatment groups; CMH test
 
[REDACTED]
 
[REDACTED] Gated hierarchical testing will be conducted.

Hypothetical estimand for secondary categorical endpoints (EU only)	
Achievement of at least a 1-grade improvement from baseline in GL severity at maximum frown based on:
 
 • Subject assessment using FWS at Hour 24 • Investigator assessment using FWS at Hour 24 	Subjects who discontinue study prior to Hour 24 assessments, or who do not have FWS assessments will be included in the analysis as a hypothetical scenario in which they had not missed the FWS assessments	
Response rates and rate differences between AGN-151586 and placebo treatment groups; CMH test
 
[REDACTED]
 
[REDACTED] Gated hierarchical testing will be conducted.

Hypothetical estimand for secondary categorical endpoints (US FDA)	Mostly satisfied or Very satisfied on the Facial Lines Satisfaction Questionnaire (FLSQ) follow-up version Item 5 (overall satisfaction) for GL at Day 7	Subjects who discontinue study prior to Day 7 assessments for the FLSQ follow-up assessments will be included in the analysis as a hypothetical scenario in which they had not missed the FLSQ assessments	
Response rates and rate differences between AGN-151586 and placebo treatment groups; CMH test
 
[REDACTED]
 
[REDACTED] Gated hierarchical testing will be conducted.

Estimand Label	Attributes of the Estimand		
	Variables (Endpoints)	Handling of Intercurrent Events	Statistical Summary
Hypothetical estimand for secondary categorical endpoints (US FDA; EU)	
 Mostly satisfied or Very satisfied on the FLSQ follow-up version Item 5 (overall satisfaction) for GL at Hour 24 Mostly satisfied or Very satisfied on the FLSQ follow-up version Item 4 (natural look) for GL at Day 7 	Subjects who discontinue study prior to Hour 24 or Day 7 assessments for the FLSQ follow-up assessments will be included in the analysis as a hypothetical scenario in which they had not missed the FLSQ assessments	Response rates and rate differences between AGN-151586 and placebo treatment groups; CMH test [REDACTED] [REDACTED] Gated hierarchical testing will be conducted.
Hypothetical estimand for secondary categorical endpoints (EU)	Mostly satisfied or Very satisfied on the FLSQ follow-up version Item 5 (overall satisfaction) for GL over time*	Subjects who discontinue study or who do not have FLSQ follow-up version Item 5 will be included in the analysis as a hypothetical scenario in which they had not missed the FLSQ assessments	Response rates and rate differences between AGN-151586 and placebo treatment groups; CMH test [REDACTED] [REDACTED] Endpoint will be evaluated outside of the gated hierarchical testing.
Hypothetical estimand for secondary categorical endpoints (EU only)	
 Key: Achievement of at least a 20-point improvement from baseline in FLO-11 total scores for GL at Day 7 Achievement of at least a 4-point improvement from baseline in FLO-11 Item 10 (look angry) for GL at Day 7 Achievement of at least a 4-point improvement from baseline in FLO-11 Item 5 (look less attractive) for GL at Day 7 	Subjects who discontinue study prior to Day 7 assessments or who do not have FLO-11 Day 7 assessments will be included in the analysis as a hypothetical scenario in which they had not missed the FLO-11 assessments	Response rates and rate differences between AGN-151586 and placebo treatment groups; CMH test [REDACTED] [REDACTED] Gated hierarchical testing will be conducted.

Estimand Label	Attributes of the Estimand		
	Variables (Endpoints)	Handling of Intercurrent Events	Statistical Summary
Hypothetical estimand for secondary categorical endpoints (EU only)	
 Subject-reported global assessment of change in GL based on the GAC-GL over time* 	Subjects who discontinue study or who do not have the GAC-GL assessments will be included in the analysis as a hypothetical scenario in which they had not missed the GAC-GL assessments	Mean and mean differences between AGN-151586 and placebo treatment groups; ANCOVA   Endpoints will be evaluated outside of the gated hierarchical testing.
Hypothetical estimand for secondary continuous endpoints (EU only)	
 Time to the first ≥ 1-grade improvement from baseline on the FWS according to subject assessment (DB period)* Time to the first ≥ 1-grade improvement from baseline on the FWS according to investigator assessment (DB period)* Time to return to baseline FWS criterion[†] according to subject assessment of FWS (DB period)* Time to return to baseline FWS criterion[†] according to investigator assessment of FWS (DB period)* 	Subjects who discontinue study or do not have FWS assessments will be included in the analysis as a hypothetical scenario in which the assessments were conducted as if they had not missed the FWS assessments	 Endpoints will be evaluated outside of the gated hierarchical testing.

ANCOVA = analysis of covariance; CMH = Cochran-Mantel-Haenszel; EU = European Union; FDA = Food and Drug Administration; FLO-11 = 11-item Facial Line Outcomes; FLSQ = Facial Line Satisfaction Questionnaire; FWS = Facial Wrinkle Scale; GAC-GL = Global Assessment of Change in Glabellar Lines; GL = Glabellar lines; US = United States

* Endpoints will be excluded from hierarchical testing.

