Hypothetical estimand for secondary categorical endpoints (EU only)	Subject-reported global assessment of change in GL based on the GAC-GL over time*	Subjects who discontinue study or who do not have the GAC-GL assessments will be included in the analysis as a hypothetical scenario in which the assessments were conducted as per protocol	Responses and mean and their differences between AGN-151586 and placebo treatment groups at each time point; CMH test and ANOVA models Endpoints will be evaluated outside of the gated hierarchical testing.
Hypothetical estimand for secondary continuous endpoints (EU only)	 Time to the first ≥1-grade improvement from baseline on the FWS according to subject assessment* Time to the first ≥1-grade improvement from baseline on the FWS according to investigator assessment* 	Subjects who discontinue study or do not have FWS assessments will be included in the analysis as a hypothetical scenario in which the assessments were conducted as per protocol	Endpoints will be evaluated outside of the
	 Time to return to baseline FWS according to subject assessment of FWS (double-blind period)* Time to return to baseline FWS according to investigator assessment of FWS (double-blind period)* 		gated hierarchical testing.

ANOVA = analysis of variance; CMH = Cochran-Mantel-Haenszel; EU = European Union; FDA = Food and Drug Administration; FLO-11 = 11-item Facial Line Outcomes; FLSQ = Facial Line Satisfaction Questionnaire; FWS = Facial Wrinkle Scale; GAC-GL = Global Assessment of Change in Glabellar Lines; GL = Glabellar lines; US = United States

* Endpoints will be excluded from hierarchical testing.

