2.4 Sample Size Determination

Approximately 600 subjects will be randomized into the study in a 3:1 ratio, yielding approximately 450 subjects in the AGN-151586 group and 150 subjects in the placebo group in the treatment period.

For the US FDA, a sample size of 600 subjects will have > 99% power to detect a difference on Day 7 between the AGN-151586 group and the placebo group using the composite endpoint of \geq 2-grade improvement, [REDACTED]

For the EU regulatory agencies, a sample size of 600 subjects for the ITT population will have >99% power (and the subgroup population of an estimated 360 subjects will provide > 99% power) to detect a difference between the AGN-151586 group and the placebo group at Day 7 for each of the coprimary endpoints, [REDACTED]

Sample size calculations were based on the two group χ^2 two-sided test of equal proportions using nQuery (Version 7.0) at a 0.05 level of significance.

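### GAC-GL: the SAP's visible analysis is a mean difference by ANCOVA without the protocol's response/CMH analysis, and at 3:1 a common-variance standard error would be miscalibrated if the arms differ in spread

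*SAP*

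**What the plan says.** Protocol Section 3.1, Table 2, gives the statistical summary for the GAC-GL as "Responses and mean and their differences between AGN-151586 and placebo treatment groups at each time point; CMH test and ANOVA models". That is two analyses, one of responses and one of means, at each time point.

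In SAP Section 9.4.2, Table 2, the visible summary for the same endpoint is "Mean and mean differences between AGN-151586 and placebo treatment groups; ANCOVA". Text after that phrase is missing from the public copy. The row still carries the label that begins "Hypothetical estimand for secondary categorical endpoints (EU only".

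SAP Section 9.4.1 describes a two-item instrument, one item at rest and one at maximum frown, each with its own score: "The response options are scored on a 7-point numerical rating scale". The endpoint listings in SAP Sections 3.2, 9.4.2 and 13.0 do not say which item is meant.

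For secondary endpoints in general, SAP Section 9.4.2 says that "the proportion of responders will be analyzed using the CMH test" and assigns ANCOVA to continuous variables. On size and allocation, SAP Section 2.4 says "Approximately 600 subjects will be randomized into the study in a 3:1 ratio".

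**The concern.** There are two connected points.

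The first is a difference between the documents. Among the rows of SAP Table 2 labelled categorical, the GAC-GL row is the only one whose visible summary has neither response rates nor a CMH test. SAP Section 1.0 says that changes from the protocol's analyses are detailed in Section 14.0, but no legible entry there records or explains this one. A reader of the visible plan would expect a mean difference on a 7-level scale and not the proportion of subjects who reported improvement.

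The second is the standard error of that mean difference. The usual ANCOVA estimates one residual variance for both arms. A bounded change score under an effective treatment rarely has equal spread: one arm may gather at no change while the other spreads over the improved grades, or the active arm may gather at the top while placebo is spread out. With equal arms, pooling the variances does little harm to the SE of a difference. With 3:1 arms it does not average out. What is at stake is whether a reported interval for the GAC-GL mean difference covers at its stated level, visit by visit.

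**Working it through.** **Inputs from the documents.** N = 600 at 3:1 (SAP 2.4), so 600 × 3/4 = 450 active and 600 × 1/4 = 150 placebo. This reproduces the plan's own split. The power statement of more than 99% in SAP 2.4 concerns the primary endpoints; no figure is given for the GAC-GL.

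**Inputs assumed.** The documents give no SD and no expected distribution for the GAC-GL, so the ratio r = placebo SD / active SD is varied from 0.5 to 2.0. Covariates and imputation are left out.

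**Formulas**, with sA and sP the active and placebo SDs:

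- Pooled variance: sp² = (449·sA² + 149·sP²)/598
- Model SE² = sp²·(1/450 + 1/150), which is approximately sA²/150 + sP²/450
- True SE² = sA²/450 + sP²/150
- Coverage of a nominal 95% interval = 2·Φ(1.96 × model SE / true SE) − 1

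The approximate form shows the mechanism: pooling attaches each arm's variance to the other arm's sample size.

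**Worked cases with sA = 1.**

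- r = 0.5: sp² = (449 + 149 × 0.25)/598 = 0.813. Model SE = √(0.813 × 0.00889) = 0.0850. True SE = √(1/450 + 0.25/150) = 0.0624. Ratio 1.36.
- r = 2: sp² = (449 + 149 × 4)/598 = 1.747. Model SE = √(1.747 × 0.00889) = 0.1246. True SE = √(1/450 + 4/150) = 0.1700. Ratio 0.73.

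| r (placebo SD / active SD) | model SE / true SE | coverage of nominal 95% |
|---|---|---|
| 0.5 | 1.36 | 99.3% |
| 0.7 | 1.19 | 98.0% |
| 0.8 | 1.12 | 97.1% |
| 1.0 | 1.00 | 95.0% |
| 1.25 | 0.90 | 92.1% |
| 1.5 | 0.82 | 89.3% |
| 2.0 | 0.73 | 84.9% |

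**Check on 7-category scores.** Three invented distributions, scored +3 to −3 and given below as percentages from best to worst, were simulated 20,000 times at 450/150:

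- A: active 45, 30, 13, 9, 2, 1, 0; placebo 2, 4, 10, 78, 4, 1, 1
- B: active 75, 18, 4, 3, 0, 0, 0; placebo 5, 10, 20, 50, 10, 3, 2
- C: active 30, 25, 20, 20, 3, 1, 1; placebo 0, 3, 10, 82, 4, 1, 0

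| | SD active / placebo | pooled SE / Welch SE | coverage, pooled | coverage, Welch | difference in pooled SEs / Welch SEs |
|---|---|---|---|---|---|
| A | 1.131 / 0.766 | 1.21 | 98.2% | 95.1% | 19.1 / 23.0 |
| B | 0.698 / 1.158 | 0.79 | 87.9% | 95.0% | 29.4 / 23.2 |
| C | 1.323 / 0.539 | 1.46 | 99.6% | 95.2% | 12.8 / 18.6 |

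A separate simulation of 4,000 replicates added a baseline-severity covariate to a linear model. It used three further assumed distributions, with active/placebo SDs of 0.87/0.45, 0.46/0.85 and 1.11/0.34. The model SE was 1.34, 0.75 and 1.54 times the true SE. The formulas above give 1.35, 0.755 and 1.55 from the same SDs. Intervals with HC3 standard errors covered 94.7% to 95.4%.

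**The case against.** The strongest reply is that much of the relevant text cannot be seen. The SAP version history for version 3.0 mentions the GAC-GL together with a responder definition, the list of additional efficacy endpoints in SAP Section 3.3 is blacked out, and wording after ANCOVA is missing in Sections 9.1, 9.4.2 and Table 2. A reader might therefore infer too much in saying that the responder analysis has been lost; the documents do not establish that. One part of the point does survive. SAP Section 9.5 analyses additional endpoints as observed, while Section 9.2 applies multiple imputation to all secondary endpoints. A responder analysis placed among the additional endpoints would not by itself deliver the protocol's secondary analysis.

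A reader might also infer a breach of SAP Section 9.1, where "categorical variables will be analyzed using Cochran-Mantel-Haenszel (CMH) test". That rule applies unless another method is specified, and the GAC-GL row specifies one. The mismatch is with the protocol and with the row's own label.

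Nor do the documents show that the error bars are wrong. No SD is given, the visible text does not state a common variance, and the visible row does not promise a confidence interval. The direction of error depends on which arm is more dispersed, and in several of the assumed cases the interval is conservative. All of this stands, and it makes the variance point conditional.

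Finally, the GAC-GL is a non-key EU secondary endpoint outside the testing hierarchy (SAP Section 13.0). This also stands, and it limits the consequence.

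**Conclusion.** The point holds in a conditional form. The visible SAP analysis of the GAC-GL omits the response/CMH part that the protocol planned, and no legible log entry says why.

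If the ANCOVA uses a common variance and the arms differ in spread, the SE of the mean difference is between 1.36 and 0.73 times the true value for SD ratios of 0.5 to 2.0, and coverage lies between about 99% and 85%. The SD ratios are assumptions. Unequal spread is nevertheless the reasonable expectation for a bounded 7-level score when a large effect is anticipated: the protocol cites a Phase 2b investigator-rated responder rate of about 95%, on a different measure. The direction may also change between visits.

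It would be too strong to infer that the efficacy conclusion is at risk. If the two arms had the same distribution, their variances would be equal and the test would keep its level. In simulated cases A to C the difference was at least 12.8 standard errors under either formula. The effect is on interval coverage, and no gated claim rests on it. It is worth correcting because the better method is simple.

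**What to change.** - In SAP Section 9.4.2 and the GAC-GL row of Table 2, state that the SE and confidence interval of the mean difference come from a heteroscedasticity-consistent (HC3) or unequal-variance estimator at each double-blind visit. Compute it within each imputed data set before combining. If the redacted text already says this, nothing more is needed here.
- Restore the protocol's response/CMH analysis at each visit, using the sponsor's own responder definition, or add a cross-reference if it already stands in redacted text. The protocol gives no cut-off for response, so this review does not propose one.
- Report the at-rest and maximum-frown items separately and say so in the endpoint listing.

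The cost is SAP wording and at most one further table, with no new data. The downside is that intervals become wider at visits where placebo is the more variable arm; where active is the more variable, they become narrower.
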